6.4 Pharmacokinetic/Pharmacodynamic Analyses Set(s)

All subjects who received AMG 301 and had at least one PK sample collected will be included in the Pharmacokinetic Analysis Set. These subjects will be evaluated for pharmacokinetics unless significant protocol deviations affect the data analysis or if key dosing, dosing interruption or sampling information is missing.

7. Planned Analyses

7.1 Interim Analysis and Early Stopping Guidelines

After about 50% of the subjects have been enrolled in the DBTP and completed the week 12 visit, multiple independent, unblinded interim analyses will be performed for administrative purposes for future study planning and development based on the interim effect size results for the primary endpoint. The results of these interim analyses will not affect the execution of this study. The maximum number of interim analyses will be no more than 5.

These administrative interim analyses will be conducted by an independent group that is internal to Amgen (eg, Clinical Therapeutic Area Head and 2 statisticians) and separate from the study team; the study team will remain blinded to the specific results.

Subject-level treatment group assignment will only be available to Amgen personnel who comprise the external team until the study has been unblinded for the primary analysis.

The primary endpoint (ie, change from baseline period in monthly migraine days) and the following secondary endpoints will be included: achievement of at least 50% reduction in monthly migraine days, and change from baseline period in monthly acute migraine-specific medication days. No safety data will be included.

An internal unblinded team will perform the interim analyses and provide the interim report. Members will review all available safety and efficacy data periodically after at least 50% of the subjects have been enrolled and have completed the week 12 visit. The internal team will have access to subjects' individual treatment assignments. To minimize the potential introduction of bias to the conduct of the study, members of the interim analysis group will not have any direct contact with study center personnel or subjects.

An independent Data Review Team (DRT) will review and make recommendations regarding the safety of the study participants throughout the DBTP and until treatment assignment is unblinded to the study team. The DRT will be composed of Amgen staff that are external to the study team and will include a clinician, a safety physician, and a biostatistician. Summaries of data at the treatment group level will be prepared and presented by an independent biostatistician at the DRT meeting. A study DRT charter will be developed to guide membership, procedures, and meeting timing.

7.2 Primary Analysis

The objective of the primary analysis will be to test the primary efficacy endpoint once the primary completion milestone is achieved after the last subject reaches the last visit in the DBTP, and all data are collected for the primary endpoint. At this time, the study will be unblinded and all efficacy and safety analyses will be conducted and reported by treatment group for both CM and EM. **Safety data collected during safety follow-up before the data cutoff date for the primary analysis will also be summarized.**

The following hypothesis for the primary endpoint will be tested for each AMG 301 treatment group (420 mg SC injections Q2W, 210 mg SC injections Q4W) compared to placebo using the generalized linear mixed effects model:

- Clinical Hypothesis: In subjects with CM **and** EM, AMG 301 reduces the monthly migraine days from the baseline period, compared to placebo

To maintain a family-wise type I error at 0.10 for the testing of the primary endpoint, the pair-wise comparison will be tested for both (1) AMG 301 420 mg SC injections Q2W versus placebo and (2) AMG 301 210 mg SC injections Q4W versus placebo, each at an alpha level of 0.05.

7.3 Final Analysis

The final analysis will be completed after study completion is reached, after the last subject reaches the last visit during the safety follow-up period, and all data are collected for the study. **The safety analyses will be summarized for both the DBTP and safety follow-up phase combined.** In addition, any changes made in the database for data from the double-blind treatment period and following the completion of the primary analyses will be noted. Any changes to data from the double-blind phase will be listed and an assessment will be made to determine if any of the primary analyses should be rerun. Where this is the case, any changes in results and/or study conclusions will be documented in the clinical study report (CSR).

8. Data Screening and Acceptance

8.1 General Principles

The objective of the data screening is to assess the quantity, quality, and statistical characteristics of the data relative to the requirements of the planned analyses.

8.2 Data Handling and Electronic Transfer of Data

The Amgen Global Study Operations-Data Management (GSO-DM) department will provide all data to be used in the planned analyses. This study will use the RAVE database.

8.3 Handling of Missing and Incomplete Data

Subjects may miss specific data points for a variety of causes. In general, data could be missing due to a subject's early withdrawal from study, a missed visit, or inability to evaluate an endpoint at a particular point in time. For this study, most of the efficacy endpoint will be collected via eDiary and subjects could miss entering several days of data in each monthly interval. The general procedures outlined below describe what will be done when a data point is missing.

In general, the PAS will be used without any subject-level imputation for missing data for the primary and secondary endpoints, except for proration performed for the eDiary measurements, as described below. The sensitivity analyses for both primary and secondary analyses will use non-responder imputation for categorical endpoints and multiple imputation with the assumption of missing not at random (MNAR) (with control- based pattern imputation) for the continuous endpoints.

Missing eDiary data in the calculation of monthly measurements about subjects' migraine and non-migraine headaches and missing daily scores of impairment day based on MPFID will be handled based on the degree of completion during the month.

For the eDiary, if at least 14 out of 28 monthly days are not missing, then the monthly frequency measurements (eg, migraine days, headache days, migraine attacks) will be prorated based on the number of days with available information using the following formula:

Number of observed migraine days *28/Number of information days in interval,
where an information day is a diary day or headache day.

For each MPFID daily diary domain, if greater than 50% of the items within a domain are not missing, the mean of the item scores that are present for that day will be used to impute a score for the missing item(s). Otherwise, no domain score will be calculated; the domain score will be considered missing.

Table 8-1. Handling of Missing and Incomplete eDiary Data

Monthly Endpoint	Condition	Proration Method (does not need to be rounded)
Monthly frequency measurements (including migraine days, headache days, migraine attacks, acute headache medication treatment days, acute migraine-specific medication treatment days)	If diary days in entire baseline or interval post baseline ≥ 14 (including retrospective eDiary days), then do proration; Else monthly measurement is set to missing [A diary day is a day with all headache related questions completed retrospectively or not]	Number of observed migraine days * 28/ Number of information days in interval [information day is a diary day or headache day]
Monthly average of severity of migraine pain (1-3 scale)	If diary days in entire baseline or interval post baseline ≥ 14 (including retrospective eDiary days), then calculate the average; Else missing	Arithmetic mean of the observed pain scores of qualified migraine headaches over the monthly interval
Monthly average of MPFID domain scores	If days with observed daily domain score in interval ≥ 14 then calculate the average; Else missing	Arithmetic mean of the observed daily domain score over the monthly interval
Monthly impairment day for Everyday Activity and Physical Impairment domains and overall	If days with observed daily domain score in interval ≥ 14 then do the proration; Else missing	Number of observed impairment days * 28/ Number of days with domain score in monthly interval

Completely missing COAs and subject-completed assessments (eg, HIT-6, MIDAS) scheduled to be collected at office visit at certain assessment will not be imputed.

Missing safety endpoints and antibody data will not be imputed, except for adverse event dates as described in [Section 8.3](#).

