#### **10.2.4 Handling of Missing and Incomplete Data**

Subjects may miss specific data points for a variety of causes. In general, data could be missing due to a subject's early withdrawal from study, a missed visit, or inability to evaluate an endpoint at a particular point in time. For this study, most of the efficacy endpoint will be collected via eDiary and subjects could miss entering several days of data in each monthly interval. The general procedures outlined below describe what will be done when a data point is missing.

In general, the PAS will be used without any imputation for missing data for the primary and secondary endpoints, except for proration performed for the eDiary measurements, as described below. The sensitivity analyses for both primary and secondary analyses will use non-responder imputation for categorical endpoints and last observation carried forward analyses for the continuous endpoint.

Missing eDiary data in the calculation of monthly measurements about subjects' migraine and non-migraine headaches and missing daily scores of impairment day based on MPFID will be handled based on the degree of completion during the month.

For the eDiary, if at least 14 out of 28 monthly days are not missing, then the monthly frequency measurements (eg, migraine days, headache days, migraine attacks) will be prorated based on the number of days with available information using the following formula:

Number of observed migraine days \*28/Number of information days in interval, where an information day is a diary day or headache day.

For each MPFID daily diary domain, if greater than 50% of the items within a domain are not missing, the mean of the item scores that are present for that day will be used to impute a score for the missing item(s). Otherwise, no domain score will be calculated; the domain score will be considered missing.

Missing COAs and subject-completed assessments (eg, HIT-6, MIDAS) scheduled to be collected at office visit at certain assessment will not be imputed.

Missing safety endpoints and antibody data will not be imputed, except for adverse event dates as described in [Section 10.2.4.1](#).

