A migraine attack is an episode of any qualified migraine headache or migraine specific medication intakes for aura only. The following rules will be used to distinguish an attack of long duration from two attacks, or to distinguish between attacks and relapses:

- a) A migraine attack that is interrupted by sleep, or temporarily remits, and then recurs within 48 hours will be considered as one attack and not two.
- b) An attack treated successfully with medication but with relapse within 48 hours will be considered as one attack.

A migraine attack lasting more than 48 hours will be counted as one attack.

Monthly Migraine Attacks

Number of migraine attacks during each 28-day period. Monthly migraine attacks at baseline are the number of migraine attacks in baseline period. Days without eDiary data are handled by proration according to Section 8.3.

Response

At least a 50% (or at least 75% or 100%) reduction from baseline in monthly migraine days over the last 4 weeks of the DBTP.

Monthly Acute Headache Medication Treatment Days

Number of days on which acute headache medications are used as recorded in eDiary during each 28-day period. Monthly acute headache medication treatment days at baseline are the number of acute headache medication treatment days in the baseline period. Days without eDiary data are handled by proration according to [Section 8.3](#).

Monthly Acute Migraine-specific Medication Treatment Days

Number of days on which migraine specific medications are used during each 28-day period. Migraine-specific medications include two categories of medications: triptan-based migraine medications and ergotamine-based migraine medications. Monthly migraine-specific medication treatment days at baseline are the number of migraine-specific medication treatment days in the baseline period. Days without eDiary data are handled by proration according to Section 8.3.

Monthly Average Severity of Migraine Pain

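### The single proration formula in SAP Table 8-1 uses observed migraine days as numerator for all five monthly frequency measures, contradicting the SAP 5.1.1 definitions of four of them, including a secondary endpoint

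*SAP*

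**What the plan says.** The first row of SAP Table 8-1 is labelled "Monthly frequency measurements (including migraine days, headache days, migraine attacks, acute headache medication treatment days, acute migraine-specific medication treatment days". Its only formula is "Number of observed migraine days * 28/ Number of information days in interval". The row's condition is at least 14 diary days in the interval ("including retrospective eDiary days), then do proration; Else monthly measurement is set to missing").

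The running text of SAP 8.3 says "then the monthly frequency measurements (eg, migraine days, headache days, migraine attacks) will be prorated based on the number of days with available information" and follows with the same formula, "Number of observed migraine days *28/Number of information days in interval". Protocol 10.2.4 has the same sentence and the same numerator. In both texts the measures are listed as examples, and neither medication measure is among them. The reach to all five measures therefore comes from Table 8-1.

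SAP 5.1.1 defines each measure by what it counts. For acute migraine-specific medication treatment days this is "Number of days on which migraine specific medications are used during each 28-day period", limited to triptan-based and ergotamine-based drugs. The same entry sends days lacking diary data to Section 8.3 for proration. No other proration formula for these measures appears in the readable text.

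**The concern.** The definition and the derivation rule do not agree. A programmer who takes the definition from SAP 5.1.1 counts medication days. One who takes the formula from Table 8-1 counts migraine days, whichever of the five measures is being derived.

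The change in monthly acute migraine-specific medication days is a secondary endpoint (SAP 2.1). It is also one of the three endpoints in the unblinded interim analyses (protocol 10.4.1.1, SAP 7.1). Under the literal rule its prorated values are migraine-day values. An independent programmer who validates against Table 8-1 could not reproduce the endpoint that SAP 5.1.1 defines. Headache days, attacks and acute headache medication days have the same problem.

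**Working it through.** There is no stated figure to reproduce, so the check sets the rule against the definitions and then applies both to assumed diary counts.

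**1. Is the numerator meant to be generic?** The last row of Table 8-1, for MPFID impairment days, prorates with its own count of impairment days. The table therefore names a specific numerator where it means one, and the first row names migraine days.

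**2. Algebra.** Let M be observed migraine days, D the observed count of the measure being derived, and I the information days.
- Literal rule: M × 28 / I for all five measures.
- Own count: D × 28 / I.
- Error in a prorated level: (M − D) × 28 / I.

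**3. Direction of the error in the level.**
- Migraine-specific medication days: SAP 5.1.1 counts any day of triptan or ergotamine use during aura or for headache as a migraine day. So D ≤ M, and the literal value is equal or too high. In a 28-day interval each migraine day without such a drug adds 28/I days: 1.0 at I = 28, 1.17 at I = 24 and 2.0 at I = 14.
- Headache days: every migraine day is a headache day. So D ≥ M, and the literal value is equal or too low.
- Attacks and acute headache medication days are different counts, so their values are wrong whenever they differ from M.

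**4. Worked subject.** The documents give no diary counts, so these are assumed: 28 information days at baseline and 24 in the week 12 interval, with proration applied to both.

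| Measure | Observed, baseline / week 12 | Own count, prorated | Literal rule |
|---|---|---|---|
| Migraine days | 12 / 9 | 12.0 to 10.5 (−1.5) | 12.0 to 10.5 (−1.5) |
| Headache days | 16 / 12 | 16.0 to 14.0 (−2.0) | 12.0 to 10.5 (−1.5) |
| Migraine attacks | 6 / 5 | 6.0 to 5.83 (−0.17) | 12.0 to 10.5 (−1.5) |
| Acute headache medication days | 11 / 8 | 11.0 to 9.33 (−1.67) | 12.0 to 10.5 (−1.5) |
| Migraine-specific medication days | 8 / 6 | 8.0 to 7.0 (−1.0) | 12.0 to 10.5 (−1.5) |

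For medication days at week 12: 9 × 28/24 = 10.5 against 6 × 28/24 = 7.0. The difference is 3 × 28/24 = 3.5. For a subject with the same migraine days and no triptan or ergotamine use, the literal week 12 value is 10.5 against 0. Criterion 106 item 3 admits subjects who cannot take these drugs.

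**5. How far the rule reaches.** Table 8-1 prorates whenever there are at least 14 diary days, with no exception for complete diaries. The opening of SAP 8.3 and the SAP 5.1.1 entries confine proration to missing data. For the medication endpoint in the worked subject:
- *Table 8-1 scope.* Both intervals are prorated: 12.0 to 10.5, change −1.5, identical to the primary endpoint (own count −1.0). With a complete 28-day week 12 diary: 12.0 to 9.0, change −3.0, against −2.0.
- *Missing-days scope.* The complete baseline keeps its own count and only week 12 is prorated: 8.0 to 10.5, change +2.5, against −1.0. With a complete week 12 diary: 8.0 to 6.0, change −2.0, and no error.

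Intervals with missing days are wrong on either scope. The error in the change has no fixed sign. It can also vanish: with 14 information days at week 12, 5 migraine days and 3 medication days, the Table 8-1 scope gives 12.0 to 10.0 and the own count gives 8.0 to 6.0, both −2.0.

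**The case against.** The strongest reply is that the intended numerator is clear from the rest of the SAP. SAP 5.1.1 defines each measure, at baseline as well, by its own count, and its change formula for medication days subtracts those counts. SAP 5.6 lists the change in medication days separately from the changes in migraine days and headache days. SAP 9.4 summarises baseline medication days once for all subjects and once for users only, a distinction that needs non-users to have none. In SAP 8.3 and protocol 10.2.4 the formula can be read as a template written out for the first measure named. All of this stands, and it makes a drafting error the likely explanation. It does not supply a correct formula: Table 8-1 lists the medication measures by name and prints a numerator that contradicts their definitions.

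A reader might infer more than the documents support:
- *That every subject-month is affected.* This holds only on the Table 8-1 scope. SAP 5.1.1 and the opening of SAP 8.3 limit proration to missing days.
- *That the derived endpoint would carry no information on medication use.* A day of triptan or ergotamine use for aura or headache is itself a migraine day, so the migraine-day count partly reflects it.
- *That everyone admitted under criterion 106 items 2 and 3 would be credited with medication days they never had.* Item 2 covers past intolerance and does not establish that neither drug class was used during the study. The statement is safe only for subjects who in fact recorded no use.

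**Conclusion.** The rule as printed is wrong for four of the five measures in its row, and it contradicts SAP 5.1.1. A literally prorated value of migraine-specific medication days equals prorated monthly migraine days. It exceeds the true level by 28/I for each migraine day on which no such drug was taken: 3.5 days in the worked subject, and 10.5 days for the non-user. Prorated headache days would be equal or too low, and attacks and acute headache medication days would also be wrong. The primary endpoint and the 50% responder endpoint are unaffected, because migraine days is their correct numerator.

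The sizes rest on assumed counts and illustrate the rule; they do not estimate any effect on the trial's results. It would go too far to conclude that the secondary test was in fact a copy of the primary test. The code appendix is blacked out, nothing readable shows how the derivation was programmed, and a programmer working from the definitions would probably have used the right count. On the missing-days scope the two endpoints would not coincide even under the literal formula. The point is a probable drafting error in an operative derivation rule for a secondary and interim endpoint.

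**What to change.** In Table 8-1, the SAP 8.3 text and protocol 10.2.4, replace the numerator so that the formula reads: number of observed days (or attacks) of the measure being derived × 28 / number of information days in the interval. The protocol formula can instead be clarified in the SAP. It would help to list the numerator for each of the five measures. Then check the derivation programs, including those for the interim analyses, against the corrected formula.

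With the own count, a complete 28-day interval returns the count itself (6 × 28/28 = 6), so for those intervals the conflict over when to prorate no longer matters.

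The cost is one line of wording in each place, or an SAP clarification in place of a protocol change, plus the program check. No new data are needed, and the primary analysis does not change.

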8.3.1 Missing and Incomplete Dates

Missing or incomplete dates will be listed unless imputed as follows:

Incomplete start date of an adverse event or concomitant medication taken will be handled by following rule:

	Missing	Imputation	Exception
Start date (Adverse event, concomitant medication)	Day	01	Default to Study Day 1 if an adverse event starts the same year and month as Study Day 1 and the flag indicates that the adverse event started on or after the first dose on the Adverse Events eCRF
	Day/Month	01 JAN	Default to Study Day 1 if an event started the same year as Study Day 1 and the flag indicates that the adverse event started on or after the first dose on the Adverse Events eCRF
	Day/Month/Year	No imputation	

8.3.2 Missing Baseline Evaluation

Baseline values are defined in [Section 5.3 “Baseline Assessment”](#). Missing baseline evaluations will not be imputed.

All subjects included in the primary analysis set will have baseline monthly rate or monthly baseline average of migraine and non-migraine headaches related measurements after applying proration rule defined in [Section 8.3](#) since only subjects with $\geq 80\%$ compliance of eDiary use during baseline will be eligible for randomization.

8.3.3 Missing Post-baseline Evaluation in the DBTP

Primary analysis of continuous efficacy endpoints during the 12-week randomized DBTP will be conducted using the generalized linear mixed model on observed data without subject-level imputation.

In sensitivity analyses of primary and secondary efficacy endpoints during the 12-week DBTP, missing continuous monthly efficacy endpoints will be handled using multiple imputation (MI) with the assumption of missing not at random (MNAR) (with control-based pattern imputation). The continuous monthly efficacy endpoints will be computed as the mean over the last four weeks of the DBTP based on the observed and imputed values.

In the non-responder imputation (NRI) method, post-baseline missing dichotomous efficacy endpoints (**responder [Yes/No] based on $\geq 50\%$, $\geq 75\%$ and 100% reduction from baseline in monthly migraine days**) during the DBTP will be imputed as

non-responder at each corresponding time point. The dichotomous endpoints derived based on the mean change from baseline over the last 4 weeks of the DBTP will be imputed as non-responder if the mean change from baseline over the last 4 weeks of the DBTP is missing.

If the proportion of missing data for the primary endpoint is high (eg, > 20%), further analyses will be performed to

- examine the frequency and reason of missing data
- determine if there are any patterns in the missing data
- distinguish true missing values from other unknown values (eg, due to measurement or sample processing error)

